5.3 Selection and Timing of Dose for Each Patient

Rituximab and obinutuzumab will be dosed according to the same regimens. The two doses of both drugs will be administered approximately 2 weeks apart, on Day 0 at week 1 and on day 14 (± 2 days). A window of ± 2 days is permitted to accommodate potential scheduling conflict.

5.4 Patients will be considered treatment failures if the glucocorticoid dose has to be increased either during the prednisone taper or after remission because of a disease relapse or if any other treatment for ANCA-associated vasculitis is prescribed to treat a disease relapse. The patients who experienced treatment failure with detectable B cells (≥ 5 cells/ μ L) will be offered open-label obinutuzumab accompanied one to three intravenous methylprednisolone pulses (1000 mg each) starting on or within 10 calendar days of obinutuzumab followed by oral glucocorticoid dosing at the discretion of the investigator (but not to exceed the original specified glucocorticoid tapering regimen) to control the disease. Patients who experience a treatment failure and B cells are still depleted should be treated according to best medical judgment. Patients who respond to the re-treatment and achieve clinical remission will enter the maintenance phase and be evaluated every 3 months until the study completes. Any patient who experiences treatment failure should continue with study follow-up visits per the schedule of assessments through the end of study. **Method of Assigning Patients to Treatment Groups**

The study will be conducted at 3 investigative sites in the US and will likely involve variable numbers of patients at each site. Enrollment will be on a competitive basis but will not exceed 15 patients (50% of the total) per site. Eligible patients who have completed the screening period and meet all study inclusion/exclusion requirements will be randomized in a 1:1 ratio to receive investigational products. Patients will be assigned to treatment groups in sequential order as they qualify for the study following the randomization procedure provided in Section 5.4.9. Randomization will be stratified according to the baseline renal function (≥ 30 or < 30 mL min $^{-1}$ per 1.73 m 2 by Chronic Kidney Disease Epidemiology Collaboration (CKD-Epi) equation without the race factor (Levey et al., 2009) ([Appendix 4](#)).

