5.4.9 Randomization Procedures

After the patient has been registered into the study, the values of the stratification factors will be recorded, and the patient will be assigned to one of the following treatment groups using the Pocock and Simon dynamic allocation procedure which balances the marginal distributions of the stratification factors between the treatment groups (Pocock SH, Simon R. Sequential Treatment Assignment with Balancing for Prognostic Factors in the Controlled Clinical Trial. *Biometrics* 31(1):103-115, 1975, Mar.)

- Treatment 1: Two infusions of obinutuzumab of 1000 mg each administered 2 weeks apart.
- Treatment 2: Two infusions of rituximab of 1000 mg each administered 2 weeks apart.

After treatment assignment has been ascertained by the registration/randomization application as specified in section 5.4.3, the registration specialist will notify the designated unblinded data manager/nurse/pharmacist at the patient's institution. The name of this contact person is to be entered in the designated space on the eligibility checklist, so the Registration Office personnel have it for each patient at the time of registration. Make sure this contact person will be available at the time of registration so they can take a call from the registration specialist if necessary. This contact person may not be involved in assessing adverse events or any other outcome measure and should not be the same person listed on the Eligibility Checklist Form as the person completing the form. The last page of the Eligibility Checklist Form should provide the sources of communication, either fax or email, and the appropriate contact information. The registration specialist will then communicate the treatment assignment to the designated unblinded contact at the patient's institution.

The unblinded pharmacist will maintain records that indicate the identity of the patient and their corresponding treatment assignment.

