9.2 Determination of Sample Size

PRRR is an exploratory proof-of-concept study to evaluate the potential utility of obinutuzumab for the treatment of PR3-ANCA associated vasculitis. We anticipate the proportion of patients in the obinutuzumab group that will achieve complete remission and ANCA negativity is 0.55 and the proportion of patients in the rituximab group that will achieve complete remission and ANCA negativity is 0.30; the planned sample size of 30 patients in two equal size groups is not powered to test the hypothesis that obinutuzumab is superior to rituximab. No sensitivity analyses (e.g., to account for missing data) and no adjustment for multiple comparisons will be conducted. Nominal p-values will be used to examine any trends in the endpoint.

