9.5 Primary Efficacy Endpoint

The primary efficacy endpoint is defined as the proportion of patients achieving complete remission and ANCA negativity at month 6. Complete remission is defined as:

- BVAS/WG of 0; and
- No requirement for glucocorticoids for treatment of PR3-ANCA associated vasculitis beyond the prescribed 16-week prednisone taper.

Patients must achieve a complete remission as defined above and be ANCA-negative at month 6 in order to meet the primary efficacy endpoint.

The primary efficacy analysis is to compare the proportion of patients assigned to the obinutuzumab group who meet the primary efficacy endpoint criteria at month 6 to the proportion of patients assigned to the rituximab group who meet the primary efficacy endpoint criteria at month 6.

Descriptive statistics (number and percent of subjects meet the primary efficacy endpoint criteria) will be reported by treatment group.

The following null (H_0) and alternative (H_a) hypotheses will be tested using Fisher's Exact test the mITT analysis set:

$$H_0: \pi_{\text{obinutuzumab}} - \pi_{\text{rituximab}} = 0$$
$$H_a: \pi_{\text{obinutuzumab}} - \pi_{\text{rituximab}} \neq 0$$

π obinutuzumab: proportion of patients assigned to the obinutuzumab group who achieve complete remission and ANCA negativity in 6 months

II rituximab: proportion of patients assigned to the rituximab group who achieve complete remission and ANCA negativity in 6 months

The above null hypothesis will be tested using Fisher's Exact test. Two-sided Newcombe-corrected 95% confidence intervals of the risk difference between treatments with respect to the primary efficacy endpoint success rate will also be presented. It is not expected that the null hypothesis will be rejected at a two-sided 0.05 level of significance given the proof-of-concept nature of the study and given the small sample size; trends seen between treatment groups in the primary endpoint rate will be used to define future studies.

The above analyses on the primary efficacy endpoint success rate will be performed when all subjects have completed 6 months of follow-up (or would have completed 6 months of follow-up) had they not withdrawn.

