9.7 Secondary Endpoints

No sensitivity analyses and adjustment for multiple comparisons will be conducted for the secondary endpoints. Nominal p-values will be used to examine any trends in these endpoints. The analyses will be carried out on the ITT and mITT populations, with no imputation for missing data. The secondary endpoints are:

- To compare the proportion of subjects who achieve sustained complete remission at months 6, 12 and 18 (BVAS/WG = 0 without glucocorticoids) by administration of obinutuzumab or rituximab. These comparisons will be carried out using Fisher's Exact test.
- To compare the time to treatment failure through month 18 by administration of obinutuzumab or rituximab; patients will be considered treatment failures if the glucocorticoid dose has to be increased because of a disease relapse either during the prednisone taper or after the remission is achieved. A disease relapse is defined as an increase in the BVAS/WG of 1 point or more accompanied by a decision on the part of the investigator to increase treatment for PR3-AAV. Time-to-treatment failure will be compared between treatments using the log-rank test; Kaplan-Meier plots of time to treatment failure through 18 months will be generated for each randomized treatment group; patients not experiencing treatment failure will be censored at last known follow-up for these analyses.

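### Randomisation is stratified by baseline eGFR, but the efficacy analyses the protocol names ignore the stratum; if renal function predicts outcome, the pooled tests are conservative

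*Combined protocol and SAP*

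**What the plan says.** Section 5.4 (Method of Assigning Patients to Treatment Groups): "Randomization will be stratified according to the baseline renal function", with a cut at 30 mL/min/1.73 m² by the CKD-EPI equation without the race term. Patients "will be randomized in a 1:1 ratio to receive investigational products".

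Section 5.4.9 records the stratification values at registration and assigns treatment by the "Pocock and Simon dynamic allocation procedure which balances the marginal distributions of the stratification factors between the treatment groups". It speaks of factors in the plural, but eGFR is the only one named anywhere.

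Section 9.5 (primary endpoint): "The above null hypothesis will be tested using Fisher's Exact test", together with a Newcombe interval for the risk difference. Section 9.7 uses Fisher's test for sustained complete remission at months 6, 12 and 18, and then: "Time-to-treatment failure will be compared between treatments using the log-rank test". The Synopsis repeats these choices. None of these places mentions the stratum, a stratified test or covariate adjustment.

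Section 9.2 gives expected success rates of 0.55 and 0.30 and adds that "the planned sample size of 30 patients in two equal size groups is not powered to test the hypothesis". Sections 3.1.3 and 9.1 defer to a full SAP, to be final before the month-6 analysis; that SAP is not in the text available.

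**The concern.** With a single factor, balancing its margin balances the arms within each eGFR stratum. The treatment contrast then carries almost none of the difference in outcome between strata, but a pooled test still counts that difference as noise. If eGFR below 30 predicts a worse (or better) outcome, the pooled test rejects less often than its nominal level under the null and has less power than a test within strata.

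The trial will be read through nominal p-values and trends, and 9.5 says those trends will shape later studies. With 15 patients per arm, precision that the allocation has already secured should not be dropped without a reason.

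**Working it through.** **No figure to reproduce.** The plan states no power. Exact enumeration of two-sided Fisher at 15 v 15, rates 0.55 v 0.30 (9.2) and alpha 0.05 (9.1) gives power 15.2%, and true size 1.7% at a common rate of 0.30. Much of the conservatism is therefore Fisher's discreteness, before any stratum is considered.

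**Inputs that must be assumed.** Number per arm with eGFR below 30: 2, 4 or 6. Success rates (obinutuzumab/rituximab), low then high eGFR stratum:
- moderate effect: 0.35/0.15 and 0.62/0.355
- strong effect: 0.20/0.05 and 0.68/0.39
- no effect: 0.55/0.30 in both

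**What pooling leaves in the variance.** With share w in the low stratum, the between-stratum part of an arm's variance is w(1−w)(p_high − p_low)².
- Moderate, 4 per arm: w(1−w) = (4×11)/225 = 0.196. Sum over arms: 0.196×(0.27² + 0.205²) = 0.0225. Overall rates are 0.548 and 0.300, so the pooled variance is 0.548×0.452 + 0.300×0.700 = 0.458. Share: about 5%.
- Strong, 6 per arm: w(1−w) = 0.24. Sum: 0.24×(0.48² + 0.34²) = 0.083. Overall rates are 0.488 and 0.254, so the pooled variance is 0.439. Share: about 19%.

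**Power, same kind of test on both sides.** The stratified exact test takes the total successes on obinutuzumab, conditions on each stratum's margins, and refers the total to the convolution of the two hypergeometric distributions. All tables were enumerated:

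| Below 30, per arm | Stratum effect | Fisher | Stratified exact | Gain (points) |
|---|---|---|---|---|
| 2 | moderate | 15.6% | 18.6% | 3.0 |
| 2 | strong | 16.9% | 23.5% | 6.6 |
| 2 | none | 15.2% | 16.4% | 1.2 |
| 4 | moderate | 14.2% | 17.4% | 3.2 |
| 4 | strong | 13.4% | 20.9% | 7.5 |
| 4 | none | 15.2% | 16.3% | 1.1 |
| 6 | moderate | 13.2% | 16.0% | 2.8 |
| 6 | strong | 10.9% | 18.7% | 7.8 |
| 6 | none | 15.2% | 15.8% | 0.6 |

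The stratum rates are held fixed, so the overall rates are close to 0.55 v 0.30 at 4 per arm but drift at 2 and 6; compare across rows, not down columns. The stratified exact test lost power in no case, and its size was at most 2.4%.

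**How much is stratification, how much is discreteness.** The gain with no stratum effect comes only from a finer reference distribution. The mid-p versions, pooled to stratified at 4 per arm, give 24.8% to 26.0% (moderate), 24.5% to 29.3% (strong) and 25.9% to 26.1% (none). With 2 per arm, even the strong case moves only from 29.0% to 29.4%.

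**Log-rank.** Assumed: 10 of 30 below 30, treatment hazard ratio 0.4. In 6,000 simulated trials per setting, unstratified to stratified power was 30.3% to 32.1% (stratum hazard ratio 2), 31.2% to 36.2% (ratio 3) and 28.6% to 27.9% (no effect). At ratio 3 the size was 3.3% unstratified and 5.2% stratified. A separate run of 4,000 trials per setting gave 36% to 44% at ratio 3 (size 3.1% v 5.2%) and 37.2% v 36.8% with no effect. The baseline hazard is also assumed, and absolute power depends on it; the pattern is the same in both.

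**One data set.** With 8/15 v 4/15, Fisher p = 0.264. If the low-eGFR patients are 0/3 v 0/3, the stratified exact p is 0.220; if they are 2/3 v 1/3, it is 0.271.

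**Intervals.** With 10–35% of patients below 30 and stratum odds ratios of 1 to 8, mean Newcombe width (no continuity correction) was 0.60–0.61, against 0.61–0.62 for a stratified Newcombe interval: not narrower in any setting. A stratified score interval at 4 per arm averaged 0.635 (moderate), 0.620 (strong) and 0.643 (none), against about 0.605 for Newcombe.

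**The case against.** The strongest reply has four parts.

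1. **Nothing turns on it.** The trial is declared exploratory and unpowered, 9.5 does not expect rejection, and the omission errs on the conservative side. All true. It limits the size of the point, but a nominal p-value meant to show trends should still come from the better-matched test when that costs nothing.

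2. **Section 9 is a summary, with a full SAP to follow.** Also true, and the SAP may restore the stratum. But 9.5 and 9.7 name specific tests, and the promise of a later document does not alter them.

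3. **The gain is discreteness in disguise.** Partly right. The mid-p comparisons show that stratification alone adds little unless the stratum effect is strong, and most of the step from Fisher (13–15%) to stratified mid-p (26–29%) at 4 per arm is due to mid-p. Mid-p is a separate choice, and its gain should not be credited to stratification.

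4. **No document shows that eGFR predicts this endpoint.** Correct. Choosing it as the only balancing factor suggests that it was thought relevant, but that is not evidence of an effect. In simulations with minimisation and no stratum effect, the stratified p-value was lower than Fisher's in 34–36% of trials and higher in 42–51%; with an odds ratio of 8 it was lower in 61–78% and higher in 8–17%.

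**Conclusion.** The point holds in a limited form. The factor used to allocate patients is missing from every efficacy test and interval that 9.5 and 9.7 name, and no reason is given. If renal function predicts outcome, the pooled tests are conservative. Under the assumed stratum sizes and effects, the loss of exact-test power is about 3 to 8 points (about 1 point with no effect), and unstratified log-rank size falls to about 3% at a stratum hazard ratio of 3. Even with stratification the exact test's power stays at 16–24% in the cases run, so the trial remains unpowered, as 9.2 says.

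A reader might infer that the planned p-values are too high and the planned intervals too wide as a matter of course. The documents do not support that. They give neither the share of patients below 30 nor any link between eGFR and the endpoint, a single p-value can move either way, and stratifying did not narrow the Newcombe interval in any setting tried. Nor is type I error inflated.

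**What to change.** In 9.5 and 9.7, and in the full SAP:

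- Test the binary endpoints with an exact conditional Cochran-Mantel-Haenszel test, using the eGFR stratum recorded at randomisation.
- Use a log-rank test stratified by the same factor for time to treatment failure.
- Report a stratum-weighted risk difference, with its interval method named, beside the planned Newcombe interval.
- State that a stratum that is empty, or has patients in only one arm, adds no information to the stratified test. This is plausible with 30 patients, and more so in the mITT set.
- Keep the pooled analyses as supportive.
- Decide on mid-p separately and give its own reason.

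The cost is wording: the stratum is already recorded at registration under 5.4.9, and the SAP is to be finalised before the month-6 analysis. If renal function turns out to be unrelated to outcome, the price is under 1 point of log-rank power (0.7 and 0.4 points in the two runs) and a slightly wider interval for the stratum-weighted difference than the uncorrected Newcombe interval.

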5.4.1 Pre-Registration of a Subject

To pre-register a subject, access the Mayo Clinic Research Registration Application at [REDACTED]. The Research Registration Application is available 24 hours a day, 7 days a week. Back up and/or system support contact information is available on the website. If unable to access the website, email the Research Registration Office at [REDACTED] between the hours of 8:00 am and 4:30pm Central Time (Monday through Friday).

The instructions for the application are available on the Mayo Clinical Office of Clinical Trials web page [REDACTED]

[REDACTED] and detail the process for completing and confirming patient pre-registration. Prior to registering/randomizing, this pre-registration process must be completed in its entirety and a Mayo Clinic subject ID number must be available as noted in the instructions.

5.4.1.1 – Verification of Materials

Prior to accepting the pre-registration, the registration/randomization application will verify the following:

- IRB approval at the registering institution
- Patient Pre-Registration Eligibility
- Existence of a signed informed consent form
- Existence of a signed authorization for use and disclosure of protected health information.

5.4.1.2 – Pre-registration Tests/Procedures

Pre-registration tests/procedures must be completed with the guidelines specified on the test schedule.

5.4.2 Documentation of IRB approval

Documentation of IRB approval must be on file in the Research Registration Office before an investigator may register any patients.

In addition to submitting initial IRB approval documents, ongoing IRB approval documentation must be on file (no less than annually) with Research Site Management (Fax: [REDACTED] or email [REDACTED]). If the necessary documentation is not submitted in advance of attempting patient registration, the registration will not be accepted, and the patient may not be enrolled in the protocol until the situation is resolved.

When the study has been permanently closed to patient enrollment, submission of annual IRB approvals to the Research Registration Office is no longer necessary.

5.4.3 Registration and Randomization of a Subject

To register and randomize a patient, access the Mayo Clinic Research Registration Application at [REDACTED] The registration/ randomization application is available 24 hours a day, 7 days a week. Back up and/or system support contact information is available on the website. If unable to access the website, email Research Registration Office at [REDACTED] between the hours of 8 a.m. and 4:30 p.m. Central Time (Monday through Friday).

Prior to initiation of protocol treatment, this process must be completed in its entirety and an MCCC subject ID number must be available as noted in the instructions. It is the responsibility of the individual registering the patient to confirm the process has been successfully completed prior to release of the study agent. Patient registration via the registration/randomization application can be confirmed in any of the following ways:

- Contact Research Registration Office at [REDACTED]. If the patient was fully registered and randomized, the Research Registration Office staff can access the information from the centralized database and confirm the registration.
- Refer to the Research Registration Application training course on the Mayo Clinic Office of Clinical Trials webpage (link above) for instructions on viewing the patient's registration & randomization confirmation.

5.4.4 Correlative Research

An optional correlative research component for biomarker sample testing is part of this study. At the time of registration, the following will be recorded:

- Patient has/has not given permission to store and use his/her sample(s) for future research of Anti-Neutrophil Cytoplasmic Antibody (ANCA-)Associated Vasculitis at Mayo.
- Patient has/has not given permission to store and use his/her sample(s) for future research to learn, prevent, or treat other health problems.
- Patient has/has not given permission for MCCC to give his/her sample(s) to researchers at other institutions.

5.4.5 Treatment on Protocol

Treatment on this protocol must commence at an approved designated institution under the supervision of a medically licensed physician. All required baseline symptoms must be documented and graded.

5.4.6 Treatment Start

Treatment cannot begin prior to registration and must begin \leq 14 days after registration.

5.4.7 Pretreatment

Pretreatment tests/procedures (See Section 7.2.1) must be completed within the guidelines specified on the test schedule.

5.4.8 Study Drug

Study drug is verified as being available on site. Obinutuzumab and rituximab will be shipped directly to each site from Genentech. (See Section 5.10 for Study drug storage and accountability). Each participating institution will be responsible for monitoring drug supplies and will order additional supplies as needed from Genentech.

5.4.9 Randomization Procedures

After the patient has been registered into the study, the values of the stratification factors will be recorded, and the patient will be assigned to one of the following treatment groups using the Pocock and Simon dynamic allocation procedure which balances the marginal distributions of the stratification factors between the treatment groups (Pocock SH, Simon R. Sequential Treatment Assignment with Balancing for Prognostic Factors in the Controlled Clinical Trial. *Biometrics* 31(1):103-115, 1975, Mar.)

- Treatment 1: Two infusions of obinutuzumab of 1000 mg each administered 2 weeks apart.
- Treatment 2: Two infusions of rituximab of 1000 mg each administered 2 weeks apart.

After treatment assignment has been ascertained by the registration/randomization application as specified in section 5.4.3, the registration specialist will notify the designated unblinded data manager/nurse/pharmacist at the patient's institution. The name of this contact person is to be entered in the designated space on the eligibility checklist, so the Registration Office personnel have it for each patient at the time of registration. Make sure this contact person will be available at the time of registration so they can take a call from the registration specialist if necessary. This contact person may not be involved in assessing adverse events or any other outcome measure and should not be the same person listed on the Eligibility Checklist Form as the person completing the form. The last page of the Eligibility Checklist Form should provide the sources of communication, either fax or email, and the appropriate contact information. The registration specialist will then communicate the treatment assignment to the designated unblinded contact at the patient's institution.

The unblinded pharmacist will maintain records that indicate the identity of the patient and their corresponding treatment assignment.

